4 BACKGROUND AND RATIONALE

4.1 Epidemiology

Sleep apnoea is a chronic condition where the person stops breathing for more than ten seconds (an apnoea) or shallow breathes for more than ten seconds (a hypopnea). Both events reduce the oxygenation of the blood. Less than 20% of sleep apnoea is caused by brain commands (central sleep apnoea) with more than 80% due to obstruction of the airways (obstructive sleep apnoea - OSA)¹.

OSA is a common, treatable condition. Recent research indicates that 936 million globally have mild-to-severe OSA, with 425 million with moderate-to-severe OSA¹. Even in first-world countries, the vast majority (up to 80%) of those affected remain undiagnosed and therefore untreated²⁻⁴. The lack of an appropriate level of case identification is driven by three factors: patients are frequently unaware of their own symptoms of sleep apnoea since they are often identified either by a bed partner or family member; clinicians in most medical specialties, and especially within primary care, do not have access to a simple sleep apnoea screening device; and health care professionals often lack the necessary training to identify high risk people and screen for early intervention. An accessible diagnostic technology and improved knowledge of the risk factors leading to sleep apnoea are therefore crucial to properly screen those with the highest risk.

1.5 million people in the UK have OSA. Up to 4 per cent of middle-aged men and 2 per cent of middle-aged women in the UK have OSA. It also affects 3 per cent of children in the general population; and as many as 50 per cent of children who are obese or have specific disabilities or other health conditions. Older people are even more at risk, with 15 to 20 per cent of those aged 70 and more estimated to have the condition. This means that OSA is the most common chronic respiratory condition, and the numbers affected are believed to be rising due to more people being overweight.⁴ Currently, due to the cost of the diagnostic equipment, OSA is diagnosed at specialist sleep clinics. More than 25% of the people referred to these centres are snorers, who could be screened out by Apne-Scan, releasing much needed specialist diagnostic capacity.

Due to the proven association between OSA and cardiovascular or metabolic pathology, it is clear that undiagnosed moderate-to-severe OSA results in significant additional healthcare costs. In the UK out of the 1.5 million people believed to have OSA, currently only 330,000 are treated⁴. In September 2014, the Office of Health Economics Consulting and British Lung Foundation (now Asthma+Lung UK) concluded that increasing treatment rates to 45% of OSA patients (effectively all moderate-to-severe OSA) would save the NHS £28 million per year and produce 20,000 QALYS annually⁵. Additionally, they estimated a reduction of 40,000 road accidents annually due to a reduction in fatigue. Case-control studies in the UK and USA have consistently shown that OSA patients use more healthcare resource, with more frequent hospital admissions in the years before diagnosis, when compared to subjects

without OSA⁶⁻¹¹. This is exemplified by a case-control study of 97 obese patients with severe OSA which reported that in the 2 years prior to diagnosis, OSA patients spent 251 nights in the hospital compared with 90 nights for the control group (p,0.001)⁶.

4.2 Current screening/diagnostic methods

Current screening and diagnostic devices for sleep apnoea are complicated, expensive and do not measure the breath pathway, they measure proxies for cessation of or reduction in respiration. They are also complicated and, even with the recent introductions of WatchPat™ and AcuPebble™, the median cost of current diagnostics is still in the region of £2-£3K per device plus consumables. This includes ResMed's NOX T3 diagnostic device illustrated above. Polysomnography (PSG) diagnostic devices can cost over £10,000 per unit depending on functionality. Some of the shortcomings with current 'home use' screening devices include, but are not limited to, the requirement for calibration, user error (complicated functionality), only nasal breath detection if respiration is monitored at all (most OSA patients breathe through their mouth), home damage and loss of device (not returned by patients).

ResMed's NOX T3

4.3 The Apne-Scan Device

Apne-Scan DC1 is a newly developed Class I UKCA screening device to assist clinicians to identify sleep apnoea and hypopnea. It is designed to be a low-cost, simple-to-use, single user, single use device.

4.4 Comparator Devices

ResMed's NOX T3 and Phillips Alice NightOne are market leading sleep apnoea test devices which will be used as the reference devices in this exploratory clinical study.

5.2 Previous studies

The Apne-Scan DC1 device is newly developed and has been accredited as a UKCA and CE Class 1 data collector device. Prototypes and development versions of the device have been tested both in the laboratory and overnight by people involved with its development. During these tests it was found to be safe and comfortable. It also recognised cessation of breathing (in effect, an apnoeic event) and shallow breathing (a hypopnea), delivering both the reduction in signal from the sensor during the event and also the duration of the event.

6. AIMS AND OBJECTIVES

6.1 Overall Study Aim

The overall study aim of the study is an initial assessment of whether screening patients with possible sleep apnoea using Apne-Scan DC1 can support the clinician in reaching a diagnosis of sleep apnoea and whether Apne-Scan identifies people who do not have the symptoms of sleep apnoea.

6.2 Primary Objective

The primary objective of this exploratory study is to assess Apnea-Tech's UKCA Class I Apne-Scan DC1 sleep apnoea screening device in assisting a clinical diagnosis of obstructive sleep apnoea in comparison to standard sleep apnoea test devices (ResMed NOX T3 and Phillips Alice Night One).

6.3 Secondary Objectives

- To review whether the effectiveness of Apnea-Tech's Apne-Scan DC1 low-cost screener seems to be impacted by the severity of the user's condition determined by a standard sleep apnoea test device as:
 - Mild sleep apnoea
 - Moderate sleep apnoea
 - Severe sleep apnoea
- To review whether the effectiveness of Apnea-Tech's Apne-Scan DC1 low-cost screener seems to be impacted by the severity of the user's condition determined by a standard sleep apnoea test device as:
 - Mild hypopnoea
 - Moderate hypopnoea
 - Severe hypopnoea
- To review the participant's Apne-Scan data in comparison with their oxygen saturation levels from the standard test to identify the possibility of using the Apne-Scan data to predict the user's SPO2 level.
- To assess the usability and effectiveness of the device in capturing the minimum data required for screening for sleep apnoea.

7. STUDY DESIGN

7.1 Summary of Study Design

A simple exploratory comparative study between two screening devices.

7.2 Outcome Measures

7.2.1 Research outcomes:

Primary Outcome

The primary outcome of interest is the data capture of the changing pressures in the user's breathing, whilst asleep, as recorded by the Apne-Scan DC1 device.

Note: The minimum evidence for successful completion of the study is 60 hours of breathing data captured by a minimum of 15 participants.

Secondary Outcomes

- An overall comparison of the OSA screening output from Apne-Scan DC1 with that from standard sleep apnoea test devices (ResMed NOX T3 and Phillips Alice Night One).
- A comparison stratified by the severity of the OSA indicated by standard sleep apnoea test devices.
- A comparison stratified by the severity of the hypopnoea indicated by standard sleep apnoea test devices.
- A possible first-generation algorithm, based on the Apne-Scan data, to predict the user's SPO2 level.

7.2.2 Safety Outcomes:

- Any adverse events (AEs) reported while performing the study procedures.
- Any adverse device effects (ADEs).

8. STUDY PARTICIPANTS

8.1 Study Setting

Recruitment for this research study will take place from among the patients who have been referred for diagnosis of a possible sleep disorder, possibly sleep apnoea, to the sleep clinic at the Royal Stoke University Hospital.

8.2 Study Participants

The study participants have been referred by a clinician to the sleep clinic for diagnosis of a sleep disorder, possibly sleep apnoea.

8.3 Eligibility Criteria

8.3.1 Inclusion Criteria:

The study participants must:

- Have been referred by a clinician to the sleep clinic for diagnosis of a sleep disorder, possibly sleep apnoea.
- Be about to be screened for possible sleep apnoea using a standard sleep apnoea test device.
- Be between the ages of 18 and 75 and have provided informed consent for the study.

8.3.2 Exclusion Criteria:

People who:

- Have not been referred by a clinician to a sleep clinic for diagnostic tests for sleep disorders other than for possible sleep apnoea.
- Cannot tolerate wearing a mask overnight.
- Have a neurological condition, learning or physical difficulties such that they are unable to remove a mask should they become distressed.
- Are not capable of understanding the English language version of Apne-Scan's Instructions For Use (IFU).
- Are under the age of 18 years old or over the age of 75 years old.
- Are not capable of giving informed consent.

9. SAMPLE SIZE CALCULATION

This is an exploratory study and the sample size of twenty-five participants reflects this. The outcomes of the study will be used to inform the design and outcomes of a planned, appropriately powered clinical utility and effectiveness study, which will also assess the health economic impact of Apne-Scan's use.

10. STUDY PROCEDURES

10.1 Recruitment

Potential participants for this study will be invited to take part in the study when they present at the sleep clinic at the Royal Stoke University Hospital. They will be provided with the Participant Instructions Sheet and given adequate time to consider enrolling.

10.2 Enrolment

Potential participants will be identified as follows:

Aged between 18 and 75 years.

Capable of giving informed consent.

The study team will qualify them through enquiring about their capability to remove a mask should they become distressed and their understanding of the ASDC-1's Instructions for Use.

10.3 Study Assessments

10.3.1. Schedule of Assessments

- Informed consent
- Demographic information (all standard care)
 - Age
 - Sex
 - Ethnicity
- Basic health criteria (all standard care)
 - Weight
 - Height
 - Neck circumference
 - Smoker/reformed smoker/non-smoker
 - Completes Epworth Sleepiness Questionnaire (validated)
 - Baseline Saturations at rest
- Issue of the Apne-Scan DC1 device, together with card documenting participants demographic information and basic health criteria
- Explanation to the participant of use of Apne-Scan at the same time as the standard sleep apnoea test device (either ResMed NOX T3 or Phillips Alice Night One)
- Participant uses the device overnight, at the same time as using the standard sleep apnoea test device.
- Participant completes short user questionnaire.
- Participant returns the Apne-Scan DC1 device and the completed participant questionnaire to the sleep clinic, at the same time as they return the standard sleep apnoea test device to the sleep clinic (standard care).
- Apnea-Tech analyses the data collected by Apne-Scan and provides to the clinical team.
- Output of Apne-Scan compared by clinical team to the output of the standard sleep apnoea test device used by the participant.

Schedule of study events					
Event	Enrolment	Baseline	Study	Analysis	Remarks
Clinical Data					
Informed Consent	X				
Age	X	X			
Sex		X			
Ethnicity		X			
Weight and height		X			
Neck circumference		X			
Smoking history		X			
Epworth Sleepiness questionnaire		X			
Baseline Saturations at rest		X			
Demonstration of use of Apne-Scan DC1		X			
Issue of Apne-Scan DC1 kit		X			

Apne-Scan Device					
Use of Apne-Scan DC1 overnight			X		

Post Apne-Scan Use					
Short participant experience questionnaire			X		
Return the device and questionnaire to the sleep clinic.			X		
Apne-Scan DC1 data is downloaded and secured together with clinical data and experience questionnaire, and participant's SPO2 data from the standard test for analysis				X	

10.3.2. Study Device

10.3.2.1 Description

Each Apne-Scan DC1 kit consists of the following items.

Item	Description
ASDC1	Apne-Scan DC1 device
ASDC1 IFU	Apne-Scan DC1 Instructions for Use
ASDC1 PUQ	Post use questionnaire

10.3.2.2 Infection Prevention Control

The Apne-Scan DC1 has been developed as a single user single use device. It is manufactured in a clean and ready to use state. There is no requirement for a cleaning regime, as it will only be used once.

10.3.2.3 Device Usage and Data Flow

The Apne-Scan DC1 device is a single user, single use device. It has a single flow sensor which records the pressure in the breath pathway twice per second. The definitions for diagnosing sleep apnoeas and hypopneas are all relative, based on percentage changes in sensor readings. The device will only recognise Indicative Hypopnea Events, because it does not confirm desaturation, unless the captured data can be used to accurately predict the user's SPO2 level at any time. There is no need for any calibration by the clinician or the user.

Once the device has been started, it continues to monitor the pressure in the breath pathway until the battery runs flat, which is targeted at over eight hours. The pressure readings are recorded sequentially on the internal memory for later download. They remain in the memory when the battery has run down.

After use the study participant return the used Apne-Scan DC1 and completed questionnaire, with the standard test, to the sleep clinic. The Apne-Scan data, together with the post-use questionnaire and the standard test's SPO2 level data, will be securely stored by participant number by the company and then analysed for possible apnoeas, indicative hypopneas and prediction artifacts within the Apne-Scan data of changes in SPO2 levels.

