1. LAY SUMMARY

1.1 Background

During sleep, many people have times when they breathe shallowly or completely stop. If a person stops breathing for more than 10 seconds, this is called an 'apnoea'. If shallow breathing, where the airflow drops by 30% or more, lasts for more than 10 seconds and results in the oxygen level in the person's blood decreasing by 3% or more, it is called a 'hypopnoea'. If a person has these events frequently, it disrupts their sleep and they do not awake refreshed. The tiredness can be so significant that it affects their life and can lead to accidents. These breathing events can also put strain on the heart, leading to cardiovascular conditions. These sleep disorders, usually called 'Sleep Apnoea', and can be treated for most people using 'continuous positive airways pressure', CPAP.

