1.6 How are we going to answer this question?

In this study, patients will be invited to take part if they have been referred by a clinician to the sleep clinic for a standard diagnostic test. Participation in the study does not change their NHS care pathway for their condition but could eventually lead to others being screened earlier, reducing NHS costs. If they agree to take part, at the same time as the standard test, participants will wear an Apne-Scan mask to capture details of their actual breathing. They will also complete a short questionnaire answering questions about their age, sex, weight, measurements and about using the mask. Having worn Apne-Scan overnight, they will return the device to the sleep clinic, with the standard test, for data analysis by Apnea-Tech. Apnea-Tech will not receive any personal information about the user. The company will only receive their study participant number, the data captured by their Apne-Scan device, the participant's oxygen saturation level data captured by the standard test and the participant's questionnaire answers.

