1.8 How will this research be used?

The results from analysing the data from the Apne-Scan device will be compared with those from the standard test to establish the comparability of the two methods. The study results will be published in either a journal or at a conference. Apnea-Tech will also use the results to develop a data analysis program to assist clinicians in diagnosing sleep apnoeas and hypopneas.

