13. DATA ANALYSIS

13.1 Analysis of Endpoints

13.1.1 Summary Statistics

The summary statistics produced from this exploratory study will be:

% participants successfully using the Apne-Scan DC1

Comparisons of primary diagnostic metric, AHI, between the standard sleep apnoea test device and Apne-Scan (based on recorded apnoeas and indicative hypopneas).

Primary Data Analysis

Comparison of primary diagnostic metric, AHI, between the standard sleep apnoea test device and Apne-Scan DC1.

Secondary Data Analysis

Comparison of primary diagnostic metric, AHI, segmented into mild, moderate and severe sleep apnoea, between the standard sleep apnoea test device and Apne-Scan DC1

Comparison of primary diagnostic metric, AHI, segmented into mild, moderate and severe hypopnoea, between the standard sleep apnoea test device and Apne-Scan DC1

Comparison of the participant's Apne-Scan data with their oxygen saturation levels from the standard test to identify the possibility of using the Apne-Scan data to predict the user's SPO2 level, possibly resulting in a first-generation algorithm, based on the Apne-Scan data, to predict the user's SPO2 level.

Analysis of the usability and effectiveness of the device in capturing the minimum data required for screening for sleep apnoea.

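### The company scores the Apne-Scan nights with the reference SPO2 already in hand, so the independence of the AHI comparison is not protected

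*Combined protocol and SAP*

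**What the plan says.** Section 1.6 lists what the company receives. Besides the participant number and the Apne-Scan recording, this is "the participant's oxygen saturation level data captured by the standard test and the participant's questionnaire answers". Section 10.3.2.3 gives the order of work: these data "will be securely stored by participant number by the company and then analysed for possible apnoeas, indicative hypopneas and prediction artifacts".

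The list in 10.3.1 then has two steps. First, "Apnea-Tech analyses the data collected by Apne-Scan and provides to the clinical team". Second, "Output of Apne-Scan compared by clinical team to the output of the standard sleep apnoea test device used by the participant".

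Section 13.1.1 names the AHI comparison between the two devices as the primary data analysis, with the Apne-Scan AHI counted from apnoeas and indicative hypopnoeas. It also plans to relate the Apne-Scan signal to the reference SPO2, "possibly resulting in a first-generation algorithm, based on the Apne-Scan data". Section 10.3.2.3 says the device recognises hypopnoeas only as indicative, "unless the captured data can be used to accurately predict the user's SPO2 level at any time". Section 1.8 adds that "Apnea-Tech will also use the results to develop a data analysis program".

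**The concern.** In a comparison of an index test with a reference test, each should be read without knowledge of the other. Here the party that scores the index test also made the device, and it holds part of the reference recording when it scores. A drop in the pressure signal that is hard to classify can be checked against the SPO2 trace: kept if saturation fell, discarded if it did not. Each such decision would move the Apne-Scan count towards the reference count.

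Apne-Scan has no oximeter, so the study needs to learn how far an AHI from pressure alone departs from one that requires desaturation. Scoring with SPO2 in view could hide that departure.

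Section 9 says the outcomes will inform a planned, powered study, and the safety hypothesis in section 3 is that the device does not miss moderate or severe disease. Both depend on an honest estimate of agreement. Once SPO2 has been seen, blind scoring of those nights by the same people cannot be recovered.

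**Working it through.** The plan states no figure for agreement, bias or precision, so there is nothing to reproduce. The check sets the sections side by side.

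1. **Does the scorer hold reference data?** Yes. Sections 1.6 and 10.3.2.3 and the event table in 10.3.1 all send the standard test's SPO2 to the company. The collection list in 12.2 omits SPO2, but it restricts nothing and cannot be read as overriding three explicit statements.

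2. **Is SPO2 part of the reference standard?** For hypopnoeas, yes. Section 1.1 says that shallow breathing of the required depth and length counts when it "results in the oxygen level in the person's blood decreasing by 3% or more, it is called a 'hypopnoea". For apnoeas, no: the same section defines them by cessation of breathing for more than 10 seconds. The trace therefore bears directly on the hypopnoea part of the AHI and only indirectly on the apnoea part.

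3. **Does scoring come after receipt?** Yes, on the sequence in 10.3.2.3: the files are stored together and analysed afterwards. This establishes access. It does not establish that SPO2 is used to count events.

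4. **Are the scoring rules fixed in advance?** Not in these documents. Section 1.1 gives a 30% airflow drop and 10 seconds in the lay summary. Section 10.3.2.3 says only that the definitions rest on relative changes in sensor readings. No baseline window, artefact rule, or choice between automated and manual scoring is stated.

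5. **Is there any blinding?** None is stated. The access limits in 1.6, 12.1 and 12.3 concern identity and medical notes. No section says that the reference report is final before the clinical team sees Apne-Scan output.

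6. **What does the company not receive?** The reference AHI and the scored reference events are absent from the list in 1.6, and under 10.3.1 the clinical team makes the comparison.

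7. **Can predicted SPO2 enter the AHI?** Section 13.1.1 does not plan it, because its Apne-Scan AHI counts apnoeas and indicative hypopnoeas. The exception in 10.3.2.3 would lift the indicative restriction if SPO2 could be predicted, and no section says that this is excluded in the present study. If it happened, a model fitted to these participants' reference SPO2 would feed an index compared with the reference in the same participants.

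8. **How much independent information would an SPO2 model have?** At two readings per second, 25 nights of 8 hours give 2 × 3,600 × 8 × 25 = 1,440,000 readings. The minimum evidence of 60 hours from 15 participants gives 2 × 3,600 × 60 = 432,000. The independent units are 25 people, or 15, whatever the count of readings. This bears on how an algorithm should be assessed. It says nothing about the size of any bias in the AHI comparison.

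**The case against.** The strongest defence is that access is not use. Section 10.3.2.3 defines events by changes in the sensor reading, and no section says that SPO2 is consulted when events are counted. The company does not receive the reference AHI, and the clinical team makes the comparison. The study is declared exploratory, the algorithm is only a possible first-generation one, and no accuracy claim is promised for it. The standard test belongs to the usual care pathway, and the team comparing two outputs must see both.

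Most of this stands, and it rules out several stronger readings that a reader might infer:

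- That the index and reference results are in fact not independent, or that agreement will be optimistic. The documents show an unprotected sequence, not a use of SPO2 in scoring.
- That predicted SPO2 is planned to enter the AHI. Section 13.1.1 points the other way; the exception in 10.3.2.3 merely leaves the door open.
- That the scoring program is being tuned during the study. Section 1.8 reads naturally as work done with the results afterwards.
- That an SPO2 algorithm will look accurate when it is not. This presumes a naive validation that the plan nowhere describes. Developing such an algorithm on these nights is legitimate exploratory work.
- That the study cannot inform the next one. Data capture, usability and failure rates do not depend on how events are scored.

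The defence does not answer the gap itself. Exploratory status explains a sample of 25 without a calculation. It does not explain why the scorer should hold SPO2 before scoring, when a different order would serve every objective equally well.

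**Conclusion.** The point holds as a gap in protection. Following 10.3.1 and 10.3.2.3 as written, the company scores the index test with a component of the reference standard available, under rules that are not locked, for the comparison that 13.1.1 calls primary. Agreement may be optimistic. Neither the amount nor the occurrence of bias can be derived from the documents, because they do not say how far scoring involves judgement or whether SPO2 is consulted.

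The conclusion rests on two readings: that storage of SPO2 with the recording gives the scorers access to it, and that the reference hypopnoea count uses the desaturation criterion of section 1.1. It would fall away if a separate procedure, not among these documents, already withheld SPO2 until scoring was complete.

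The change should be made before any SPO2 is released. It does not call the study's feasibility aims into question.

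**What to change.** Rewrite the sequence in 10.3.1 and 10.3.2.3, and list SPO2 in 12.2 with its point of release:

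1. The clinical team finalises the reference report for each participant before opening any Apne-Scan output.
2. The company fixes its scoring rules in writing, scores all nights from the pressure signal alone, and lodges dated, locked event lists and AHI values with the clinical team.
3. Only then is the standard test's SPO2 released to the company.
4. The AHI comparison in 13.1.1 uses the locked scores. One added sentence there states that predicted SPO2 does not enter this study's AHI, which closes the exception in 10.3.2.3.
5. Any performance figure for an SPO2 algorithm is reported either as development-only or as cross-validated by participant. Leaving out one participant at a time is one way to do the latter.

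The cost is the order of file transfers and a lock file. No participants, visits or measurements are added, and every objective is kept. SPO2 development starts slightly later, and the reported agreement may be less favourable than it would otherwise have been.
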